Documentation of training will be held on secure password protected computers at OHSU. Prior to implementation of any protocol changes, amendments will be submitted to the OHSU Institutional Review Board for approval. [name] will be responsible for continuous data and safety monitoring of all participants, and discussion of any data or safety monitoring concerns will be a routine topic of mentorship and consultation meetings. In the event there are AEs/SAEs that require medical intervention, [name], a board-certified neurologist, will be available to review events and refer them as needed.

Paper files will be stored in locked filing cabinets in restricted access offices at OHSU and will not leave the [name] lab facility. Electronic data is stored on restricted drives on the OHSU network, on OHSU approved cloud location and on encrypted computers. Electronic data will also be stored in a custom database housed on an OHSU secure server. Access to data is restricted to study personnel. Access to data requires OHSU ID/password authentication.

Upon enrollment, participants will be assigned a code that will be used instead of their name, medical record number or other personally identifying information. Electronic files for data analysis will contain only the subject code. Codes will not contain any part of the 18 HIPAA identifiers (initials, DOB, MRN) The key associating the codes and the participants personally identifying information will be restricted to the PI and study staff. The key will be kept secure on a restricted OHSU network drive in a limited access folder.

BP will be collected via Caretaker Medical VitalStream™ device, which accurately and wirelessly measures vital signs. The VitalStream™ uses an automated readout inflatable finger cuff and is connected via Bluetooth to a tablet. The CareTaker™ is completely wireless, and will relay data via Bluetooth connectivity to a tablet. It allows for secure wireless monitoring via a real-time mobile application, or remote monitoring via a Cloud Portal. For the purposes of the study, we will monitor participant data via mobile application on an encrypted Android tablet in a room adjacent to the testing room during the laboratory stressor task. There is no storage, processing or transmission of any PHI or HIPAA identifiers through VitalStream. It does not connect to OHSU network, but is transmitted via Bluetooth to an encrypted tablet.

At the completion of the study, if patients consent to sharing data in the repository, their data will be released to repository IRB #7436. See repository protocol for details about requesting, releasing, and labeling data.

10) Risks and Benefits

a) Risks to Subjects

The risk in participating in the present study is low. Participants may feel distress when reporting their PTSD symptoms or identifying their index trauma (i.e., the most salient trauma connected to their PTSD symptoms) as part of the administration of the Clinician-Administered PTSD Scale (CAPS-5). Participants may also feel discomfort or embarrassment when discussing their general experiences during the intervention conditions. They may also feel stress or frustration when completing the laboratory stressor paradigm. Participants have the right to withdraw, and may attend intervention groups and not actively participate, or may not complete MBSR home practice between sessions.

There is no discomfort associated with the collection of physiological data. The CareTaker™ device using a Velcro finger cuff attached with similar tightness to an arm cuff blood pressure monitor. A thin clear tube connects the finger cuff to a small wrist pack that houses the electronic components of the device. The CareTaker™ is completely wireless, and will relay data via Bluetooth connectivity to a tablet.

One of the potential risks of participation breach of confidentiality. It is possible that, if someone inadvertently obtained data, this could result in harm to research participants, with legal, financial, or emotional implications of the affected Veterans. We will take all possible measures to protect the security and integrity of personal health information.

b) Potential Benefits to Subjects

Veterans may find it rewarding to engage in group-based interventions in which they are encouraged to share their experiences with other veterans with similar struggles related to PTSD symptoms. They may similarly appreciate being able to share their perspectives regarding their ability and strategies for coping with symptoms. Participants may also experience reduction in symptoms of PTSD, depression, and anxiety as a result of participating in the MBSR condition.

REFERENCES

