ClinicalTrials.gov Document Upload

DOCUMENT DATE (IRB APPROVAL):

03-Jan-2024

NCT NUMBER:

NCT05938816

OFFICIAL STUDY TITLE:

Feasibility and acceptability of stress induction, physiological data collection, and Mindfulness-Based Stress Reduction among combat veterans with PTSD

INVESTIGATOR NAME:

[name], MCR

ORGANIZATION:

Oregon Health & Science University

1) Protocol Title

Feasibility and acceptability of stress induction, physiological data collection, and Mindfulness-Based Stress Reduction among combat veterans with PTSD

2) Objectives

Objectives are to gather feasibility and acceptability of key study elements (e.g., stress induction via cognitive stressor, physiological data collection including respiration, blood pressure, and heart rate, and the target intervention Mindfulness-Based Stress Reduction) among combat veterans experiencing PTSD symptoms to support a future K23 grant resubmission. Specific Aims are as follows:

Aim 1: Assess feasibility and participant acceptability of intervention and randomization procedures.

Aim 1A: Examine acceptability of MBSR via qualitative data gathered during a post-intervention focus group.

Aim 1B: Assess feasibility of recruiting and acceptability of randomizing participants to an MBSR or active control condition. Recruitment, differential retention, and home practice completion rates will be examined.

Aim 2: Assess feasibility and participant acceptability of concurrent stress induction and physiological data collection (i.e., systolic [SBP] and diastolic [DBP] blood pressure) procedures.

Aim 2A: Evaluate feasibility of stress induction via significant change in BP from baseline to stressor.

Aim 2B: Examine acceptability of physiological data collection concurrent with stressor task via focus group.

Aim 3: Evaluate sensitivity and responsiveness to change of outcome measures. Examining these qualities and pre-post changes in physiological and psychological resilience and PTSD symptoms will provide crucial information regarding relationships between the intervention and changes in relevant variables.

3) Background

Posttraumatic stress disorder (PTSD) is a significant public health concern¹ that negatively impacts quality of life and functioning,¹⁻³ is associated with increased mortality,⁴ and poses an economic burden.⁵

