Physiological resilience is another promising mechanism, and is defined as the capacity of a biological system to avoid shifting away from baseline (e.g., “reactivity”) or to return to baseline (e.g., “recovery”).⁴⁵ The sympathetic nervous system (SNS) has served as an indicator of physiological resilience among veterans.⁴⁶⁻⁴⁸ Specifically, physiological resilience is indicated by the magnitude of peripheral vasoconstriction,⁴⁸ directly related to blood pressure (BP).⁴⁹ BP has been conceptualized as an indicator of physiological resilience to negative health outcomes.⁵⁰ Combat veterans with PTSD exhibit low physiological resilience via exaggerated BP reactivity to acute stress.^{51,52} Other research has found that trauma is predictive of lower physiological resilience.⁵³ MBSR⁵⁴⁻⁵⁸ and resilience-based⁵⁹ interventions reduce BP, improve physiological resilience,^{60,61} including among military personnel.⁶² Prior to conducting a fully-powered mechanistic RCT, central research methods such as intervention, stress induction, and physiological data collection must be validated.

Feasibility and acceptability must be established. Although some studies have conducted RCTs of MBSR among veterans with PTSD,²³ feasibility and acceptability limitations remain. A systematic review currently under review by the PI found that MBIs for PTSD showed an average attrition rate of 21.3%; much higher than the general population.⁶³ The reason for this difference is unknown. A recent meta-analysis called for increased efforts to improve the feasibility and acceptability of MBIs.⁶³ Similarly, a recent review reported that data regarding adherence in MBSR (e.g. at-home meditation practice) is underreported in most studies.⁶⁴ No studies have evaluated the feasibility and acceptability of these facets of MBSR among veterans with PTSD. Further, no study has evaluated the feasibility and acceptability of a stressor task and concurrent physiological data collection in veterans. These aspects of feasibility require further study, as recent research has emphasized the need for stress induction tasks that are feasible and reproducible.⁶⁵ Given the novelty of these procedures in this population, and the potential impact of the PI’s line of research among veterans underserved by status quo interventions, this KL2 application essential. To support this line of research, this KL2 will inform the resubmission of the PI’s K23 proposal and forthcoming VA CDA.

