The long-term goal of this research is to use mechanisms identified via a fully-powered mechanistic RCT funded by NIH K23 or VA CDA to optimize a resilience-based, trauma-informed MBI. In order to secure funding and conduct this mechanistic RCT, feasibility and acceptability of the stressor paradigm and concurrent physiological data collection, as well as the MBSR and randomization procedures must be established.

4) Study Design

The design of this study is a randomized controlled interventional study. All participants will complete three in-person lab visits, consisting of computerized questionnaires, physiological data recording, and completion of a stressor paradigm. Following completion of computerized questionnaires at the baseline visit, participants will be randomized at a 1:1 ratio using covariate adaptive randomization.

Participants will be randomized to receive Mindfulness-Based Stress Reduction (MBSR; active intervention condition) or Health and Wellness Education (HWE; control condition). Both interventions include 8 weekly in-person group sessions with an additional extended session after week 8.

5) Study Population

a) Number of Subjects

This is a single center study. We will screen approximately 40 patients of which we expect to enroll 20 participants, all of whom will be veterans experiencing PTSD symptoms (PTSD symptoms will be confirmed during telephone screen). Therefore, 20 participants will sign the consent form and be included in this study.

b) Inclusion and Exclusion Criteria

Participants will be screened over phone to determine eligibility. Subjects will be aged 18-85 years. Subjects older than 85 years of age will be excluded due to their decreased ability to tolerate the experimental procedures because of potential cognitive decline and inability to sustain the attention needed for the Portland Arithmetic Stress Task (PAST), as well as the decreased ability to remain still during the intervention conditions due to musculoskeletal aches and pains and decreased flexibility frequently seen in aging.

Inclusion criteria	Exclusion criteria
Adult (18-85 years)	Pregnancy
Military veteran	Severe untreated depression, cognitive impairment, or active suicidality*
Experiencing PTSD symptoms	Life-threatening or severely disabling medical conditions
Reading and speaking in English	Excessive use of alcohol, nicotine, or cannabis†

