Aims 1&2 – Qualitative data: Focus groups will be conducted in accordance with guidelines for maximizing impact of qualitative research in feasibility studies.⁶⁶ Broad topics will cover: 1) intervention content, 2) trial design and process (including stress induction and concurrent physiological data collection), 3) outcomes, and 4) measures. These discussion topics will be tailored to fit combat veterans with PTSD symptoms via consultation with the Veteran's Engagement Group (VEG; see *Human Subject Considerations* for a description of the VEG; see also [name] LOS). A thematic analysis approach⁶⁷ will explore participant experiences to understand feasibility, acceptability, and impact of assessments, protocol, and interventions. Analysis process will consist of: 1) familiarization, 2) initial coding, 3) creating themes, 4) reviewing themes, 5) defining and naming themes, and 6) data interpretation. The PI will work with [name] (co-mentor) who has experience conducting thematic analysis of qualitative data in feasibility studies, and a trained RA to independently review focus group data.

Emerging themes will help develop a coding scheme that the team will apply independently the finalized code structure. The team will meet regularly to review coding and discrepancies to ensure inter-rater reliability.

Aim 2 – Physiological data: We will assess feasibility and effectiveness of stress induction by analyzing change in blood pressure (BP) between baseline and a cognitive stressor (see *Stress induction paradigm*

section below). BP will be collected via Caretaker Medical VitalStream™ device, which accurately and wirelessly measures vital signs. The VitalStream™ uses an automated readout inflatable finger cuff and is connected via Bluetooth to a tablet. Within-participants baseline-to-stressor task t-tests will evaluate feasibility of stress induction. Significant increases in BP from baseline to stressor will constitute effective stress induction. **Quantitative analyses will be conducted in SPSS v.28,⁶⁸ and qualitative will be conducted in NVivo.⁶⁹**

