Participants will be given the opportunity to view their heart rate and blood pressure when it is taken in the lab during the baseline condition, unless they would prefer not to. Participants will not be shown their physiological data during the stressor condition due to the expected increases resulting from cognitive stress. Besides this, participants will not have access to any other data collected as a part of this study. If participants demonstrate pathological blood pressure during the course of the study, they will be notified and referred to their PCP and/or urgent care. If blood pressure reaches hypertensive crisis (180/110) the participant will be referred immediately to the emergency department. No data will be used for clinically decision-making, nor will it be entered into participants' medical records. Referrals will be made based on generic critical blood pressure values only.

b) Data and Specimen Banking

If data or specimens will be banked in a repository for future use as part of this protocol submission, describe here (or in a separate repository protocol document) where they will be stored, how long they will be stored, how they may be accessed, and who will have access to the specimens. Describe the procedures to release data or specimens, including: the process to request a release, approvals required for release, who can obtain data or specimens, and the data to be provided with specimens.

Data will be sent to a repository maintained separately from this study. They will be stored indefinitely in repository IRB #7436. Participants will be requested to consent to sharing data in the repository which will be optional. The repository investigator and members of the [name] Cognitive Neuroscience Laboratory are allowed to access the data and will have requisite HIPAA and other trainings. Please see repository protocol for details related to that study.

8) Data Analysis

Quantitative data:

Recruitment and retention rates will be collected, compared between conditions, and evaluated in relation to previous research on MBSR recruitment and attrition. Correlations between rates of home practice completion (e.g., self-guided meditation practice) and attrition rates per condition will be examined for relationships.

Within-participants baseline-to-stressor task t-tests will evaluate feasibility of physiological stress induction. Significant increases in BP from baseline to stressor will constitute effective stress induction.

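### Aim 2A measures feasibility of stress induction by a significant BP rise, which shows effectiveness; no rate of completed, usable stressor sessions is planned

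*Combined protocol and SAP*

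**What the plan says.** Section 2 (Objectives) sets Aim 2 as: "Assess feasibility and participant acceptability of concurrent stress induction and physiological data collection". It has two parts.

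- Aim 2A, the quantitative part: "Evaluate feasibility of stress induction via significant change in BP from baseline to stressor".
- Aim 2B, the qualitative part: "Examine acceptability of physiological data collection concurrent with stressor task via focus group".

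Section 6 (Procedures, Aim 2 – Physiological data) names the test: "Within-participants baseline-to-stressor task t-tests will evaluate feasibility of stress induction". Section 8 (Data Analysis, Quantitative data) repeats this almost word for word. Both sections then give the success rule: "Significant increases in BP from baseline to stressor will constitute effective stress induction".

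The rates that the plan will examine are recruitment, retention and home practice, all under Aim 1. Section 6 also lists the stress induction and the concurrent recording among the focus-group topics, and says that the thematic analysis is meant to shed light on feasibility as well as acceptability.

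The documents contain no rate of completion of the Simple Reaction Task (SRT, the baseline) or the Portland Arithmetic Stress Task (PAST, the stressor). They also contain no rate of usable BP recordings, no signal-quality rule, no handling of missing BP values and no threshold for going on.

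**The concern.** Feasibility of a laboratory procedure is a question about how often it works: of the people who start it, how many finish with data that can be used. A paired t-test answers a different question, namely whether mean BP is higher during the stressor among those who have both values. A participant who stops the PAST, or whose finger-cuff signal is lost, simply leaves the calculation. The plan states no analysis set, but a paired test cannot use such a participant.

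Such losses are conceivable from the protocol's own text. Section 10 says that participants may feel stress or frustration during the stressor and may withdraw. Section 6 allows withdrawal for unsafe elevated BP. Losses of this kind could be related to the response being measured.

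The stressor and the recording are in the trial's title, and section 3 (Background) says that these methods must be validated before a fully powered RCT. That RCT will need to know what share of sessions yields data. As written, the plan can report that induction was feasible without giving that share.

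**Working it through.** There is no figure in the plan to reproduce: it gives no power, SD, effect size, alpha or feasibility threshold. The check is whether the stated criterion can be met when many sessions fail.

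**Inputs from the documents**
- Sample size 20 (section 5a): "Therefore, 20 participants will sign the consent form and be included in this study". The 1:1 allocation does not matter for a within-participant test pooled over arms.
- Paired t-test of BP, baseline to stressor (sections 6 and 8).
- Three stressor sessions per participant, at Lab visits 1, 2 and 3 (Study Schedule). The visit to be tested is not named.

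**Assumptions**
- Two-sided alpha 0.05. Aim 2A speaks of a change and the analysis sections of increases, so a one-sided test is also possible.
- All BP changes and SDs, and all numbers of failed sessions.
- In the power figures, losses unrelated to the BP response.

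**Step 1. One example.** Take 12 usable pairs out of 20, mean rise 8 mmHg, SD of change 8 mmHg.
- Standard error = 8/√12 = 2.31; t = 8/2.31 = 3.46 on 11 df; p = 0.005.
- Usable share = 12/20 = 60%, exact (Clopper-Pearson) 95% CI 36 to 81%.

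The criterion is met while 8 of 20 (40%) have failed.

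**Step 2. Is the example special?** The smallest observed standardised change (mean/SD of change) that reaches significance is t(0.975, n−1)/√n. Power comes from the noncentral t distribution with n−1 df and noncentrality (true standardised change) × √n.

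| Usable pairs of 20 | Smallest significant change (SD units) | Power at 0.5 | Power at 0.8 | Power at 1.0 |
|---|---|---|---|---|
| 20 | 0.47 | 56.5% | 92.4% | 98.9% |
| 16 | 0.53 | 46.5% | 84.8% | 96.2% |
| 12 | 0.64 | 35.3% | 71.4% | 88.3% |
| 10 | 0.72 | 29.3% | 61.6% | 80.3% |
| 8 | 0.84 | 23.2% | 49.6% | 68.1% |

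If the true change is one SD, the criterion is met about 80% of the time with half of the recordings lost (about 90% one-sided). If it is half an SD, that falls to 29% (43% one-sided). The test result therefore depends on the size of the effect together with the number of pairs, and the success rate of the procedure cannot be read from it.

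**Step 3. What a direct count would give.** Exact 95% CIs out of 20: 20/20, 83 to 100%; 18/20, 68 to 99%; 16/20, 56 to 94%; 12/20, 36 to 81%. The intervals are wide, but they separate a procedure that nearly always works from one that fails in 4 of 10.

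**Step 4. Which denominator.** Consent is signed on arrival at Lab visit 1, so all 20 consented participants are present there, and the intervention has not started. Pooling all 3 × 20 = 60 scheduled sessions would mix in dropout. At the 21.3% average attrition cited in section 3 (context, not a planning value), 20 × 0.213 = 4.26 participants would leave. If all left before Lab visit 2, 2 × 4.26 = 8.5 of 60 sessions (14%) would be lost without any failure of the procedure.

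**The case against.** Several points on the other side are sound.

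- **The test is tied to stress induction.** A reader might infer that the plan would declare the BP recording feasible on the strength of the t-test. No sentence does so: each statement of the test refers to stress induction. The consequence is that the recording has no quantitative feasibility measure.
- **Focus groups also address feasibility.** This is true, so the t-test is the only quantitative criterion, not the only evidence. But the focus groups yield no rate and carry no decision rule, and they take place in week 9, so they may miss people who have left.
- **The success sentence speaks of effective induction.** Sections 6 and 8 do call a significant increase effective, which is a fair description. The difficulty is that Aim 2A and the sentence naming the test call the same result feasibility.
- **A null result is informative.** A reader might infer that the rule misleads in both directions, because complete recordings with a small rise could fail it. The documents do not support that. If BP does not rise, that is a relevant answer about induction, and low power for a small rise is a separate sample-size matter.
- **The size of the rise is not wholly ignored.** The t statistic depends on the mean rise relative to its SD. What is absent is an estimate with a CI.
- **Retention is tracked.** Aim 1B would show sessions missed through dropout, but not unfinished tasks or lost signal at attended visits.
- **The example is hypothetical.** The documents give no basis for expecting 40% failure. The example shows what the criterion allows, not what is likely.

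**Conclusion.** The point holds in a limited form. The plan labels a test of effectiveness as the measure of feasibility of stress induction, and it specifies no rate of task completion or usable paired BP for either the stressor or the recording. The criterion can be met with a large share of sessions failed: p = 0.005 with 12 of 20 usable in the example, and about an 80% chance with 10 of 20 if the true change is one SD. These sizes rest on assumed effects, SDs and loss rates and on an assumed two-sided alpha of 0.05; the structural point does not. It should be corrected because it concerns an objective in the trial's title and the remedy is cheap. It does not show that the procedure will fail, or that the BP test is a poor check of whether the stressor works.

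**What to change.** 1. Make the quantitative feasibility outcome for Aim 2 the proportion of participants who complete SRT and PAST at Lab visit 1 with usable BP in both. The denominator is all 20 consented. Report it with an exact 95% CI and list the reasons for each failure.
2. Define usable BP in advance, in one line (for example, a minimum share of each task period with a valid signal).
3. Report the same proportion separately among those attending Lab visit 2 and Lab visit 3, so that dropout stays under Aim 1B.
4. Relabel the baseline-to-stressor test as evidence of effective induction. Report mean SBP and DBP change with 95% CIs, with Lab visit 1 as the main visit. At later visits the intervention is under way, and section 3 expects MBSR to improve physiological resilience, which it defines to include reactivity.

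The cost is a short log of completion and signal quality (none is described at present), the definition, and edits to Aim 2A and sections 6 and 8. No new participant procedure is needed.
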